#### 4.6 STUDY TREATMENT

Subjects will engage in an instructor-led, supervised, manual-resistance training program twice weekly. At each session, subjects will perform a variety of nonweighted resistance exercises, previously shown in a clinical trial to be safe and effective for use in pediatric populations (ClinicalTrials.gov identifier, NCT02455037) and lightly weighted exercises using barbells, and commercial neck strengthening equipment (eg, NekkDekk and/or IronNeck).

The effectiveness of the strength training regime over time will be assessed by measuring neck girth and neck strength at the beginning and end of training sessions at 6-month intervals, for as long as the subject continues the sport program or until he/she leaves the study.

# 4.7 ASSESSMENTS (BASELINE THROUGH END OF STUDY)

### Eye Tracking

Subjects' eye movements will be tracked and recorded with an SR Research Eyelink 1000 eye tracker while a 220-second video was played continuously within a square aperture moving around the perimeter of a 17" viewing monitor (aspect ratio 4:3) fixed 55cm away from the patient. The video aperture size is approximately 1/9th the area of the display monitor. The position of the eyes will be obtained at 500Hz with a stabilized chin rest to minimize head movement during the eye tracking session. All subjects will be asked to take off their glasses while being tracked. The visual stimuli are G-rated music videos, children's movie clips, and other documentary film selections. Subjects will not be spatially calibrated to the tracker to enable independent analysis of each pupil position over time. The eye tracking data will be processed to yield 89 eye tracking metrics.

#### **Cognitive** Assessments

Subjects will undergo cognitive assessments which have been previously validated in clinical research.

#### Morphometric Measurements

Height and weight will be measured using a standing scale. Head circumference will be measured at the top of pinna and neck circumference (girth) will be measured at the level of the thyroid cartilage using a flexible metric tape.

# Neck Strength Parameters

HSR# 17-4360

Neck strength (extension, flexion, left and right lateral measurements) will be assessed using a hand-held commercial dynamometer that is effective for measuring neck strength. Subjects will be permitted to rest between measurements to minimize risk of injury.

# 4.8 STUDY TIMELINE

# 4.8.1 Screening/Baseline:

Once a potential study subject is identified, informed consent will be obtained. After this, patients will be asked or undergo

• General medical questions to affirm inclusion/exclusion criteria

*If they are eligible for enrollment, they will then undergo:* 

- Training on all aspects and requirements of the study, including the neck-strengthening training program, concussion and adverse event reporting, and frequency and expectations for follow-up measurements of neck strength
- Morphometric assessments
- Cognitive evaluations
- Eye-tracking algorithm
- Neck-strength assessment

### 4.8.2 Regular Training Assessments (every 6 months):

- Review subject's impressions of the training program
- Morphometric and neck-strength measurements immediately before and after the training session

#### 4.8.3 Following a Diagnosis of Concussion (within 1 day of event):

- Review subject's general well-being
- Cognitive evaluations
- Eye-tracking algorithm
- Neck-strength assessment
- Date of last menstrual period (females only)

If concussion symptoms persist:

#### 4.8.4 Following a Diagnosis of Concussion (7 days after event):

- Review subject's general well-being
- Cognitive evaluations
- Eye tracking algorithm
- Neck-strength measurements

#### 4.8.5 Following a Diagnosis of Concussion (30, 60, 90 days after event):

- Review subject's general well-being
- Cognitive evaluations

HSR# 17-4360

# 4.9 CONCUSSION AND ADVERSE EVENT REPORTING

Athletic trainers will inform study site coordinators if a concussive event is suspected. The subject will be removed from activity and ultimately returned to activity as per their school or program protocol. The study site coordinator will immediately inform the Investigator of the event.

Monitoring of potential adverse events will be performed on a continuous and ongoing manner by the Investigator, research staff, and/or experienced athletic trainers at each study site. The nature of each adverse event, date and time of onset (when appropriate), outcome, frequency, maximum intensity, action taken, and attribution of each event will be recorded to identify those that are potentially related to the intervention (ie, the training regime). If an adverse experience increases in frequency or severity during the study period, a new record of the experience will be started.

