# 4.5 STUDY ELIGIBILITY AND ENROLLMENT

#### 4.5.1 Study Population

Subjects will be youths aged 5 to 22 who are involved in one or more academic or community-based organized contact/collision athletic sports program(s). Approximately 1500 students will be recruited from Gustavus Adolphus College, member schools of the Independent Metro Athletic Conference (IMAC) conference, and The Sanneh Foundation, and enrolled in the study. The study population will be composed of players from multiple sports, and at a broad range of competitive levels. Study-site coordinators and/or trainers will be advised of the purpose and procedures of the study and will refer subjects to the Investigator for consideration. Subjects who meet all inclusion/exclusion criteria and have appropriate consent to participate in the study may be enrolled. The study is open to all races and both genders.

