# 4.5.2 Duration of Investigation

Enrolled subjects may be followed for up to 3 years. The duration of training and assessment for subjects is anticipated to vary by sport and program. However, all subjects will HSR# 17-4360

complete the neck-strengthening training program twice weekly for the duration of time that they are enrolled in the study.

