#### 5.1 SUBJECT TRAINING

The Investigator or his/her designee will train the subjects on the correct execution of the resistance training movements, and will document this training in the subject records. Training will include the following steps and tools:

- Review all precautions and potential risks associated with participation in the training program
- Review the execution of each exercise move and the use of any applicable associated equipment
- Invite the subject to ask questions about the exercises or program

Subjects may also contact the Investigator or study-site coordinator at any time during the study to ask questions or request additional training/retraining.

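### Section 4.9 gives only a trainer-initiated route for reporting a concussion and no scheduled visit asks about interval concussions, so events outside the site program may be missed and by default analysed as non-events

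*Protocol*

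**What the plan says.** **Reporting route.** Section 4.9 begins with "Athletic trainers will inform study site coordinators if a concussive event is suspected" and continues "The study site coordinator will immediately inform the Investigator of the event". It describes no other route for a concussion. The same section adds "Monitoring of potential adverse events will be performed on a continuous and ongoing manner by the Investigator, research staff, and/or experienced athletic trainers", but that sentence concerns adverse events at the study sites, recorded in order to find those that may be related to the training.

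**Subject's part.** The baseline list in 4.8.1 includes "Training on all aspects and requirements of the study, including the neck-strengthening training program, concussion and adverse event reporting". Section 5.1 adds "Subjects may also contact the Investigator or study-site coordinator at any time during the study to ask questions or request additional training/retraining".

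**Exposure outside the site.** Section 4.5.1 describes subjects as "involved in one or more academic or community-based organized contact/collision athletic sports program(s"). Section 4.5.2 states "Enrolled subjects may be followed for up to 3 years".

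**Scheduled contacts.** The 6-month visit (4.8.2) has two items: "Review subject's impressions of the training program", and morphometric and neck-strength measurements around a training session. The annual assessments (4.1 and Table 1) take place if no head injury has been reported. Neither lists a question about concussions in the interval.

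**Use of the data.** Incidence is part of the primary objective (4.3) and the primary hypothesis (4.4). Concussion risk is to be modelled by logistic regression (6.3).

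**The concern.** Incidence is only as good as the means of finding cases. The route in 4.9 is passive and starts with a trainer's suspicion. A trainer at a study site is well placed to see an injury in that site's program, but not one in another club, in another season's sport or outside organised sport. For such an event the protocol has only the subject's or parent's memory of one baseline briefing, given for subjects as young as 5 and for follow-up of up to 3 years.

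If nobody volunteers the event, nothing later in the schedule would bring it to light. The annual assessments depend on whether a head injury was reported; they do not ask. The subject then stands among the non-concussed in the incidence model.

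This is a matter of data collection, which the protocol has to settle. No later analysis plan can recover events that were never asked about.

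**Working it through.** **Step 1: follow an outside concussion through the protocol.** Take a subject at a participating school who is concussed in a community program that is not a study site.

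| Place | Would it capture the event? |
|---|---|
| 4.9, trainer route | Only if the site trainer learns of it and suspects concussion |
| 4.9, adverse event monitoring | Directed at events at the study sites and their relation to training |
| 4.8.1, baseline training on reporting | Implies that the subject may report; gives no recipient, timing, form or reminder |
| 5.1, open contact | Possible; the stated purpose is questions or retraining |
| 4.8.2, 6-month visit | No item asks |
| 4.1 and Table 1, annual assessments | Presuppose a report; no item asks |

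Capture is possible, but no step secures it.

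**Step 2: how often staff see the subject.** Section 4.5.2 has every subject training twice weekly throughout enrolment. Footnote a to Table 1 ties training to the length of the sport program and the subject's regular athletic schedule. On the first reading, staff see subjects about twice a week; on the second, gaps between seasons are possible. The two statements need to be reconciled. Even frequent sessions do not amount to a recorded question.

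**Step 3: the plan's own figures.** Section 6.4 states an incidence of 11% and 1198 subjects before attrition.
- The attrition step reproduces: 1198 / (1 − 0.20) = 1497.5, about 1500.
- The 1198 does not reproduce exactly. Two-sided Fisher z for R = 0.25 gives ((1.960 + 0.842) / atanh 0.25)² + 3 = 123.3, so 124 concussed subjects, and 124 / 0.11 = 1127.3, so 1128. Nothing below depends on that difference.
- Expected cases at the stated size: 1198 × 0.11 = 131.8.

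**Step 4: what incomplete capture would do to incidence.** The capture share s is an assumption, and so is reading the 11% as true incidence.
- Missed cases = 131.8 × (1 − s).
- Share of recorded non-concussed subjects who are really cases = 0.11(1 − s) / (1 − 0.11s).
- Recorded incidence = 11% × s.

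| s | Missed cases | Share of recorded non-events | Recorded incidence |
|---|---|---|---|
| 0.9 | 13.2 | 1.2% | 9.9% |
| 0.8 | 26.4 | 2.4% | 8.8% |
| 0.7 | 39.5 | 3.6% | 7.7% |
| 0.5 | 65.9 | 5.8% | 5.5% |

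**Step 5: effect on the association.** Compare stronger-necked with weaker-necked subjects, with true risks p₁ and p₀ and capture shares s₁ and s₀. Assume no false positives. The recorded risk ratio is (p₁s₁) / (p₀s₀), which is the true ratio times s₁/s₀.
- Equal capture: the factor is 1. The ratio is preserved, but incidence is understated and events are lost.
- Unequal capture, for example 0.9 and 0.7: the factor is 0.9 / 0.7 = 1.29, or 0.7 / 0.9 = 0.78 the other way round.

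The sites are a college, conference member schools and a community foundation. Age, neck strength and trainer coverage could plausibly differ among them, so unequal capture is possible. The protocol has no figure for any of these by site, so neither the direction nor the size of the factor can be fixed.

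**The case against.** The strongest reply is that the protocol does not confine reporting to trainers. Subjects are trained on concussion reporting at baseline, they may contact the Investigator or coordinator at any time, and section 5 trains coordinators and site volunteers as well as trainers to recognise symptoms. With supervised sessions twice weekly, staff might hear of most concussions informally. This stands to a degree. A reader might infer that a trainer's report is the only way in; 4.8.1 rules out so strong a statement. What remains is that 4.9 does not put the subject's route into operation.

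Three other inferences go beyond the text.
- That outside concussions *are* counted as no concussion. The protocol does not say how an unreported event is classified; it is simply what happens when no report exists.
- That subjects are followed across off-seasons. Footnote a to Table 1 makes gaps possible, 4.5.2 points the other way, and 4.5.1 does not say that a second program would lie outside the participating sites.
- That the severity analysis in 6.4 loses a calculable amount of power. The protocol does not say how the cases behind the 11% were found. If they were trainer-reported, the planned case count already allows for incomplete capture. Nor would events found months later have the acute scores that a severity analysis needs, so the remedy would not restore that power.

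It is also fair to say that differential capture is a plausible risk, not a demonstrated one.

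**Conclusion.** The point holds in limited form. As written, the protocol can leave concussed subjects among the non-events of the incidence model, because 4.9 describes a trainer-initiated route only and no scheduled contact asks about the interval.

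It rests on three things in the text: participation in more than one program is allowed, follow-up may last up to 3 years, and the contents of the 6-month and annual contacts are as listed. It also rests on one judgement: a single baseline instruction is a weaker safeguard than asking.

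The size and direction of the bias are unknown. The missed-case table is conditional on assumed capture shares and on the 11% being true incidence, and no claim about power for the severity correlation is made. This is an inexpensive improvement to an outcome in the primary objective, not evidence that the incidence result would be invalid.

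**What to change.** **Data collection.** Add one item to the 6-month visit (4.8.2) and to the annual assessments: any concussion diagnosed since the last contact, in any setting, with date and diagnosing source. For young children, put it to the parent or guardian. At the annual contact, ask before deciding whether a head injury has been reported. State in 4.9 that subjects and parents may report directly, and to whom.

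**Analysis.** Count confirmed events in the incidence outcome with a flag for source (site-reported or found at interview). Repeat the incidence analysis on site-reported events only; a marked difference between the two would show that capture matters.

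**Cost.** One question at contacts already planned. Recall will be imperfect, especially in young children or by parent report over 6 months or more, and late-found events will have no acute severity data, so they inform incidence only. Some gap remains: the minimum follow-up is 4 weeks (6.2), so a subject who leaves before a first 6-month visit would not be asked. The protocol schedules no exit contact; adding one would be a new procedure with its own cost and is not needed for the main gain.

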### 5 INVESTIGATOR TRAINING

Study-site coordinators, athletic trainers at each site, and site volunteers will receive practical training in the execution of the neck-strengthening program, recognition of the symptoms of concussion, and data collection methods prior to the start of the study.

#### 5.1 SUBJECT TRAINING

The Investigator or his/her designee will train the subjects on the correct execution of the resistance training movements, and will document this training in the subject records. Training will include the following steps and tools:

- Review all precautions and potential risks associated with participation in the training program
- Review the execution of each exercise move and the use of any applicable associated equipment
- Invite the subject to ask questions about the exercises or program

Subjects may also contact the Investigator or study-site coordinator at any time during the study to ask questions or request additional training/retraining.

#### **6** EVALUATION OF OUTCOMES

#### 6.1 SAFETY

The safety of the neck-strength training program will be measured and evaluated by the incidence of injuries or other adverse events related to the study treatment.

Improper execution of the exercises will be considered in the review of potential causes for any intervention-related or possibly intervention-related adverse events during the study. Any injury or other adverse event that is determined by the Investigator or the HSR# 17-4360

Investigator's designee to be related or possibly related to the training program will be followed-up with the study subject, athletic trainer or study-site coordinator, and/or the subject's parent/guardian/legal representative to obtain wider perspective on the factors that led to the event.

### 6.2 OUTCOME ASSESSMENT

Outcomes will be assessed by an experienced researcher with neurologic and cognitive evaluations that are commercially available and validated in traumatic brain injury or cognitive dysfunction. Subjects will be followed for a minimum of 4 weeks after enrollment and a minimum of 1 week following a concussive event unless they or their legal guardians choose to leave the study.

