# 4 STUDY PROTOCOL

### 4.1 **OVERVIEW**

This project has the following goals:

- 1. Determine whether baseline measurements of neck strength correlate with the incidence, severity, and duration of concussion symptoms;
- 2. Determine whether a standardized neck strengthening training regime reduces the risk of concussion and the severity and duration of symptoms; and
- 3. Determine whether the relationships between neck strength and the clinical symptoms of concussion are independent of gender.

Subjects aged 5 to 22 who are involved in organized, academic or community-based contact/collision sports activities at Gustavus Adolphus College, member schools of the Independent Metro Athletic Conference (IMAC) conference, and The Sanneh Foundation participate in an instructor-led neck-strength training program. Subjects enrolled in the study will be followed for up to 3 years to assess whether the incidence, severity, and duration of concussion symptoms varies as a function of neck strength in young athletes. Anthropometric measurements, neck strength parameters, cognitive assessments, and an eye-tracking assessment will be performed for each subject at baseline, and at yearly intervals thereafter in the absence of a reported head injury. In addition, anthropometric and neck-strength measurements will be recorded at regular intervals during the study to quantify the effectiveness of the strength training regime. Subjects diagnosed with concussion during the study will be assessed for the severity and duration of postconcussion symptoms using eyetracking methodology and traditional cognitive assessments. Clinical outcomes will be assessed immediately following a concussive event and monitored by research staff until symptoms resolve. Data will be collected by onsite study volunteers trained by [name] or another member of the Brain Injury Research Lab staff at HCMC. All aspects of the study design will be overseen and approved by [name].

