#### Assessments and timeline

Demographic and sport history information will be collected at screening, and morphometric, cognitive, neck-strength, and eyetracking assessments will be made at baseline, and annually thereafter in the absence of a reported head injury. In addition, anthropometric and neck-strength measurements will be recorded immediately before and after training sessions at 6-month intervals to track improvements in neck strength. Subjects who experience concussion during the study will undergo assessments for eye-tracking and cognition at the time of the event; a subset of cognitive assessments will also be made on a daily basis following the event, until full recovery is achieved. If recovery is not achieved within a week, eye-tracking will be repeated. If symptoms continue to persist, additional cognitive assessments will be administered and repeated monthly until the subject fully recovers.

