# Data analysis

Repeated-measures analysis of variance (ANOVA) will be used to evaluate the effectiveness of the training program for increasing neck strength. Relationships among neck-strength parameters and concussion risk and functional outcome measures will be evaluated via logistic and linear regression models. Analyses will be adjusted for sex to evaluate whether the results are independent of gender.

SCHEDULE

Week 1: Initial visit or call prior to enrollment to obtain informed consent; Baseline assessments made within 72 hours of enrollment Weeks 4 to 52: Assessments of neck strength made at 6-month intervals (+/- 3 days)a

Weeks 4 to 52: Assessments of concussion symptoms (if applicable) until symptoms resolve.

HSR# 17-4360

	
 
Time-of-event (within 1 day of event): Cognitive and eye-tracking assessments
 
Days 1-7 after event: Daily subset of cognitive assessments
 
Day 7: Eye-tracking assessment, neck-strength measurement
 
Weeks 4, 8, and 12 after event (+/- 3 days): Cognitive assessments
 

	a The neck-strengthening training regime will be administered for the length of the subject's sport program and during the period(s) of time corresponding to the subject's regular athletic training schedule.
BLINDING	This study is nonblinded.

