### 6.3 STATISTICAL METHODS

Data accrued through this study will be reviewed with statisticians from The Minnesota Medical Research Foundation Chronic Disease Research Group. Repeatedmeasures analysis of variance (ANOVA) will be used to evaluate the effectiveness of the training program for increased neck strength. Relationships among neck-strength parameters and concussion risk and functional outcome measures will be evaluated via logistic and linear regression models. Analyses will be adjusted for sex to evaluate whether the results are independent of gender.

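### Section 6.2 guarantees only one week of follow-up after a concussion, and the linear regression named in 6.3 cannot represent a symptom duration still unresolved at last contact

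*Protocol*

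**What the plan says.** **Follow-up.** Protocol section 6.2 sets two minimums. The first is "Subjects will be followed for a minimum of 4 weeks after enrollment". The second, for anyone concussed, is "a minimum of 1 week following a concussive event unless they or their legal guardians choose to leave the study". Neither depends on whether symptoms have resolved.

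Other places go further. Section 4.1 states: "Clinical outcomes will be assessed immediately following a concussive event and monitored by research staff until symptoms resolve". In Table 1, under assessments and timeline, if symptoms persist, "additional cognitive assessments will be administered and repeated monthly until the subject fully recovers". The dated contacts are finite: the Table 1 schedule ends with "Weeks 4, 8, and 12 after event (+/- 3 days): Cognitive assessments", and section 4.8.5 lists days 30, 60 and 90.

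**Analysis.** Section 4.4 puts duration beside incidence and severity in the primary hypothesis. Section 6.3 says that the relationships of neck strength with concussion risk and "functional outcome measures will be evaluated via logistic and linear regression models". It names no method for censored data. Table 1 repeats the same models.

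**The concern.** An athlete who is still symptomatic at last contact has a duration known only to exceed the time observed. Only symptoms that outlast the exit can be cut off, so the lost information lies in the long end of a primary outcome. If the hypothesis is true, athletes with weaker necks have the longer symptoms and are cut off more often.

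Linear regression needs one completed number per subject. Entering the last observed day understates the long durations and pulls the slope on neck strength towards zero. Leaving the subject out removes long durations and lowers the estimated mean.

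Part of this cannot be repaired later. An analysis plan can choose another model, but it cannot recover a resolution date that was never collected, and the follow-up rule sits in the protocol.

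**Working it through.** **1. Do the follow-up passages agree?**
- Section 6.2: at least 1 week after the event, withdrawal excepted.
- Section 4.1 and Table 1: until symptoms resolve, with monthly repeats.
- Table 1 schedule and section 4.8.5: dated contacts to week 12 or day 90.
- Section 4.5.2: the length of training and assessment is expected to vary by sport and program.
- Section 4.5.5: a program of 4 weeks is long enough for eligibility.

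A site that stops at day 7 with symptoms ongoing meets 6.2 but not 4.1 or Table 1. A site that follows 4.1 meets both. The passages are compatible, but 6.2, the only one that states a minimum, omits the condition that matters for duration.

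**2. How many subjects carry the duration analysis?** Inputs from section 6.4: incidence 11%, 1198 subjects before attrition, about 1500 enrolled.
- 1198 / (1 − 0.20) = 1498, which reproduces the figure of about 1500.
- 1198 × 0.11 = 131.8, about 132 concussed subjects.
- 1500 × 0.11 = 165 concussed subjects.

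The protocol gives no duration distribution, so it has no figure on the censoring itself to reproduce.

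**3. Size, by illustration.** Assumed, not from the documents:
- Neck strength x is standard normal, and log T = log(m) − 0.25·s·x + s·√(1 − 0.0625)·e, with e standard normal.
- Median m is 7, 10, 14 or 21 days, and s is 0.8 or 1.0. The correlation of −0.25 is with log duration; it borrows the size that 6.4 uses for severity.
- Exit is independent of x and T and affects 20% of concussed subjects, the upper end of the 15-20% attrition.
- The last observed day is entered as the duration.

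Simulated results (one million draws), as ranges over m and s:

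| Exit pattern | Durations cut off | Fitted slope / true slope |
|---|---|---|
| 20% leave at day 7 | 10-18% | 0.80-0.85 |
| 20% leave evenly over days 7-90 | 1-6% | 0.88-0.97 |
| All observed to day 90, then stopped | 0.1-7% | 0.67-0.99 |

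The third row shows that the end of the dated visits can matter by itself when durations have a long tail.

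**4. One case by hand: m = 10, s = 0.8, 20% leaving at day 7.**
- True mean: 10·exp(0.8²/2) = 13.77 days.
- Unresolved at day 7: Φ(ln(10/7)/0.8) = Φ(0.446) = 0.672. Share cut off: 0.2 × 0.672 = 0.134, about 18 of 132.
- Part of the mean from durations above 7 days: 13.77·Φ((ln(10/7) + 0.64)/0.8) = 13.77·Φ(1.246) = 12.31.
- Mean with the last observed day used: 13.77 − 0.2·(12.31 − 7 × 0.672) = 12.25 days.
- Mean with those cases dropped: (13.77 − 0.2 × 12.31)/(1 − 0.134) = 13.06 days.

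Dropping does less harm to the slope. For day-7 exits of 10% to 50%, with medians 7-14 and s = 0.8, the ratio was 0.84 to 1.02. It costs cases and still lowers the mean.

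**The case against.** A reader might infer that 6.2 contradicts 4.1, that athletes are closed out as complete on day 7, and that cut-off durations then enter the regression as finished values. The documents support none of these.
- One week is a minimum. Early recoverers are still seen to day 7, and others may be followed for longer.
- Table 1 and sections 4.8.4-4.8.5 give further contacts to a subject whose symptoms persist. Stopping at day 7 without withdrawal would depart from that schedule.
- No passage defines a completed subject or says that the end of a program ends post-concussion follow-up.
- Section 6.3 does not name duration as a linear-regression response and does not say how unresolved cases are coded. The analysis plan, which is not shown, may do so.

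Larger effects are also tempting. With half of concussed subjects leaving at day 7, the simulated slope falls to 0.52-0.61. That scenario exceeds the stated attrition. It also exceeds what short programs could produce: if concussions are spread evenly over a program (an assumption), the last week holds 1/4 = 25% of them in a 4-week program and 1/12 = 8% in a 12-week one. A difference in bias between sites or sports cannot be shown either, because no program lengths beyond the 4-week minimum are given.

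All of these objections stand, and they limit the point to what follows. They do not remove it. Withdrawal, the end of dated visits and the end of the study leave durations unresolved however 6.2 is read, and the protocol has chosen a model class that cannot hold them.

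**Conclusion.** The point holds in a limited form. Section 6.2 is looser than 4.1 and Table 1 without strictly contradicting them. Right-censored durations can be expected in a primary outcome, and the stated model class does not accommodate them. With 20% of about 132 concussed subjects leaving early, a plausible loss is 3-20% of the slope if the last observed day is used: nearer 20% if all leave at day 7, nearer 3% if exits are spread out and durations short. If unfinished cases are dropped, the slope may be almost unaffected, but the mean is too low.

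These sizes rest on assumed log-normal durations, an assumed correlation of −0.25 and exits unrelated to strength or duration. They show the order of magnitude and are not a forecast. The point merits a change because the remedy is cheap and missing resolution dates cannot be recovered afterwards.

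**What to change.** 1. In 6.2, reconcile the minimum with 4.1 and Table 1: outcome data collection for a concussed subject continues, by remote contact if the sport program has ended, until resolution is recorded or consent is withdrawn. This concerns data collection only; return to activity stays under the school or program protocol, as 4.9 has it.
2. Add a field for the date last known symptomatic, completed for anyone who leaves, or reaches the end of the study, before resolution.
3. In 6.3, analyse duration as time to resolution, censored at that date, with a Cox or accelerated-failure-time model containing neck strength and sex, in place of linear regression. This assumes that, given those covariates, leaving is unrelated to remaining duration. Better follow-up under item 1 makes the result depend less on that assumption.

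The cost is a sentence in 6.2, one date field, one model change, and some telephone follow-up of a minority of about 132-165 concussed subjects. Withdrawals will still produce censoring, which is why item 3 is needed even with item 1 in place.
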